The available number of cases in each community is constrained by the local population and demographics as well as the pattern of hospital and emergencydepartment (ED) usage. Table 4 shows the projected number of cases in each community in three categories: total ED visits for chest pain; hospital discharges with ICD code 410 or 411; and confirmed cases of MI. Although the expected event rates in Table 4 come to 1202 per community for the 22-month trial, that rate is severely diminished by several mechanisms. First, a certain fraction of the patients discharged with 410/411 codes will present at the ED with complaints other than chest pain or will be admitted by some route not captured by the REACT sampling frame. Second, a certain fraction of cases will provide incomplete, invalid, or unusable data. Finally, a certain percentage of 410/411 diagnoses will fail to be validated. Early data showed that these mechanisms when compounded reduced the rate of usable cases by more than two-thirds, from 1202 to 375 per community. The REACT eligibility criteria were therefore revised to include all cardiac-related discharges. Broadening the criteria approximately doubled the expected sample, to 750 per community over 20 months, or a total of 15,000 usable cases.

The logistical demands of REACT measurement suggest, insofar as is compatible with sample-size requirements, that random subsampling of cases be conducted in the larger communities. Rather than lock the REACT design into a fixed subsampling scheme, the study will institute a conservative sampling plan that can be adjusted (without bias) as the data come in. In the smallest communities (two in the Washington field site and all four in the Texas site), 100% sampling will certainly be required throughout REACT. In the intermediate-sized communities, sampling will

begin at 100% but will be monitored by the Coordinating Center to determine whether "mid-course" adjustment to a smaller sampling fraction might be appropriate. In the largest communities (Worcester, MA and Eugene, OR), sampling will begin at 50% and will be similarly monitored and adjusted if necessary.

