The primary community-level endpoint of REACT is the trend in mean log delay time over the course of the trial. The individual delay times are expected to be sufficiently variable that the trend will be adequately represented by a linear slope β . The null hypothesis of REACT is that on the average β will not differ between the Intervention community and the Control community in each pair.

Delay time will be observed during a four-month baseline period and then over an 18-month intervention period (Figure 6). Each community's trend will be estimated

by simple linear regression, with all baseline observations assigned to time 0. The fitted slope *b* has a standard error asymptotically equal to $\sigma(KV_t)^{-1/2}$, where σ is the residual standard deviation of log delay time; *K* is the total number of cases collected in the community; and V_t is the variance of calendar time at which cases were observed.

The average effect of REACT is estimated by

$$\overline{d} = \sum_{j=1}^{J} \left[b_{j,Intervention} - b_{j,Control} \right] / J$$

where J=10 is the number of community pairs. \overline{d} is an unbiased estimator of the truemean difference between Intervention and Control slopes. Its variance is

$$SE^{2}(\vec{d}) = V(\vec{d}) = 2\sigma_{\beta}^{2}(1-\rho)/J + \sigma^{2}\sum_{j=1}^{J} \left[K_{j,Intervention}^{-1} + K_{j,Control}^{-1}\right]/V_{t}J^{2},$$

where σ_{β}^2 and ρ are respectively the random community-to-community variance and the intra-pair correlation between community-level linear trends.

The primary null hypothesis of the REACT trial is that there is no population ("true") mean difference between Intervention and Control slopes: $H_0:\Delta\beta = \beta\beta_{Intervention} \langle -\beta\beta_{Control} \langle = 0$, where $\langle \rangle$ indicates population expected value. The null hypothesis permits the Control slope to be nonzero and thus allows for secular trend. The alternative hypothesis is that $\Delta\beta\neq 0$; this is a two-sided alternative because it is conceivable (though not likely) that the REACT Intervention could prolong the average delay time.

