The primary hypothesis will be tested with the conventional Type I error rate of α =5% (two-sided). Sample size estimates are based on a paired *t*-test on the values of *d*, or, equivalently, using a mixed-model ANOVA with REACT group as a fixed effect (1 df). Using the *t*-test formulation, the smallest effect detectable with a specified level of power Π is given approximately by

$$\Delta\beta = SE(\overline{d})(t_{\alpha/2} + t_{1-\Pi}),$$

where t_0 demarks the specified upper tail area of the central Student distribution. The degrees of freedom for *t* are *J*-1=9.

The net end-trial effect on delay time is related to slope as follows. After L=1.5 yr of intervention, the difference in mean log delay time between Intervention and Control communities will be $\Delta y = L\Delta\beta$. The corresponding effect on the median delay time will be a multiplicative reduction by a factor of $10^{-L\Delta\beta}$, or

Relative reduction = $100\% \times (1 - 10^{-L\Delta\beta})$, Absolute reduction = $M \times (1 - 10^{-L\Delta\beta})$,

where M is the median delay time at the end of the trial in the Control communities.

C. Results and Sensitivity Analysis

Detectable effects for the primary endpoint in the primary population are shown in Table 5. Three sample sizes are considered: K=800, 600, or 400 complete, usable cases per community. The figure of 600 represents a conservative estimate, based on the above event rates and attrition parameters. For comparison, a "pessimistic" figure of 400 is included, representing the worst-case parameters with an additional 100 cases subtracted for unforeseen attrition. The "optimistic" figure of 800 per community is probably not attainable but has been included as a benchmark for comparison.

In the conservative case (600 per community), which should be easily attained with the broadened eligibility criteria, the detectable absolute reduction is between 27 and 30 min. if the initial median delay is assumed to be 2.5 hr, as much of the available data suggests. If the initial median is taken as 3.0 hr., the absolute level lies between 32 and 35 min.

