The detectable effects shown in Table 5 are not sensitive to the pair correlation of community slopes (ρ). Varying ρ between 0.4 and 0.0 changes the detectable relative reduction by no more than 1% and the detectable absolute reduction by no more than one min., regardless of the other parameters. Sensitivity to the comunity-level slope variance parameter is also slight. Between 5% and 15% variation in delay time due to random fluctuation of the community trend, the detectable relative reduction varies by 1-2%, which translates to 2-4 min. depending on the initial median.

In summary, Table 5 demonstrates that we can expect to detect a net effect of REACT in the primary population as small as 30-40 min with 80% power, regardless of the strength of pair correlation, the attained sample size, or any magnitude of random trend variability in the plausible range.

Detectable effects for secondary endpoints and for the primary endpoint in secondary populations (sub- or super-groups of the primary population) are discussed in Appendix C.

Community	ED Visits	MI Discharges (410)	410/411, All
Alabama			
Anniston (Calhoun Co.)	3667	440	1100
Tuscaloosa (Tuscaloosa Co.)	5500	660	1650
Huntsville (Madison Co.)	3667	440	1100
Opelika (Lee Co.)	4107	499	1247
Massachusetts			
Pittsfield/Dalton	2658	319	726
Westfield/W. Springfield	3343	401	796
Worcester	9686	1162	2578
Lowell	6215	746	1400
Minnesota			
Fargo/Moorhead	6087	733	1833
Sioux Falls	5500	660	1650
Eau Claire	5500	660	1650
LaCrosse	4840	587	1467
Texas			
Brownsville	2420	293	733
Laredo	2420	293	733
Tyler	1833	220	550
Lake Charles	1833	220	550
Washington			
Shoreline	1320	183	345
Olympia	1320	183	352
W. Portland/Beaverton	4620	550	1393
Eugene	4217	935	2179
Total (22mo)	80,752	10,185	24,038
Average per site	16,150	2037	4808
Avg per community	4038	509	1202

Table 4. Expected REACT Events Over 22 Months

communey					
(K)				M =2.5 hr	M =3 h
800	1.05	0.4	16	24	28
		0.2	16	24	28
		0.0	16	24	28
	1.15	0.4	17	25	30
		0.2	17	26	31
		0.0	18	27	32
600	1.05	0.4	18	27	32
		0.2	18	27	32
		0.0	18	27	32
	1.15	0.4	19	28	34
		0.2	19	29	35
		0.0	20	29	35
400	1.05	0.4	21	32	38
-		0.2	21	32	38
		0.0	21	32	39
	1.15	0.4	22	33	40
		0.2	22	34	40
		0.0	23	34	41

Relative (%)

Absolute (min)

Table 5. Detectable Reduction In Delay Time, Primary Population*

ρ

 $R_{\beta} = 10^{2\sigma_{\beta}L}$

Usable cases

per community

*80% power, 5% Type I error (two-sided)

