REACT is perfectly balanced with respect to the randomized units of analysis, the 20 communities. Given the existing imbalance in population size of the proposed pair-matched communities, it is reasonable to expect measurable imbalance in sample size per community for the two study conditions, even after the gross imbalances are mitigated by subsampling. Such imbalance is common in community trials, and may be reduced through matching on population size, through weighting community values according to the estimated inverse variance of the community value, and regression adjustment for individual-level covariates, as described above (c.f., 89,96,98,101).

REACT will use matching on community size, a sampling scheme designed to obtain essentially equal numbers of cases in each community, and regression adjustment for individual-level covariates.

5. Distributions of dependent variables

Community trials may involve outcomes measured as continuous, categorical or time-to-event variables, and these variables may display quite different error distributions at the individual level (87,94). In addition, the error distribution at the community level may not be the same as that observed at the individual level. In the case of REACT, the primary outcome will be delay time, a variable known to have a highly skewed distribution. Other important outcomes include the number of calls per unit time for emergency medical service (also highly skewed), and the proportion of events arriving at the hospital in less than six hours after symptom (binary).

The two-stage approach to analysis of data from community trials accommodates each observation-level distribution through the appropriate selection of the first-stage analysis method, in combination with appropriate transformations. Thus a log-transform could be used to convert delay time to a nearly normal distribution. At that point, the analysis could proceed in several directions. Weighted community means could be analyzed without regard to adjustment for individual or community level factors, or ordinary least squares methods could be used in a first stage to make adjustment for individual-level covariates, followed by ANOVA/ANCOVA at the second stage.

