At the individual level, if all sites are pooled, subsampling skews the ethnic composition of the overall REACT sample to some degree. These effects are detailed in Table 7. It should be emphasized, however, that a valid random subsampling scheme would not alter the ethnic balance of the sample collected in any given community. Since all primary and secondary REACT analyses, in keeping with the community randomization design, are planned at the community level, these would not be biased by subsampling.

B. Detectable effect, primary analysis

Sample size is essentially fixed in advance at both levels of REACT, on the community level at 10 pairs and at the individual level by the available number of cases or some convenient sampling fraction. The effect of the REACT Intervention in reducing delay time is by contrast difficult to predict, because comparable interventions have not previously been conducted. As a consequence, power calculations for REACT are most informatively framed with sample size, power, Type I error, and variance as fixed parameters (or, in sensitivity analysis, as independent variables) and detectable effect as the dependent variable. The requisite formulas are derived in this section. The results are tabulated and discussed in

Version 07/01/96

Section E. The sources and choices of operating parameters that enter into the formulas are detailed along with the mathematical derivation. A parameter summary is provided in Table 8.

The primary REACT endpoint is T, the delay time between onset of acute symptoms and arrival at the hospital. Because the distribution of T is skewed according to all reports from previous studies, the primary endpoint for analysis will be $y = \log_{10} T$. All other factors being equal, y will be assumed to have a normal distribution with mean μ and variance σ^2 . Thus T is log-normally distributed with median $M = 10^{\mu}$. In the log-normal distribution, approximately 95% of cases fall within a multiplicative range of $10^{\mu\pm 2\sigma}$. The multiplicative factor $R = 10^{2\sigma}$, according to pertinent data (Section II), is approximately 9. That is, 95% of delay times fall between 1/9 of the median value and 9 times the median value (Figure 7).

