In the course of REACT, y will be observed first during a four-month baseline period and then over an 18-month intervention period. Assigning all baseline observations to time t=0, where t indicates calendar time, an approximately linear decline in the mean log delay time may be assumed in each community over the course of the trial:

$$\mu(t) = \mu(0) + \beta t$$
, $0 \le t \le 1.5$ yr.

(The word "decline" is adopted for convenience; in any community the mean log delay time could conceivably go either up or down.) The slope β is the primary community-level parameter of REACT, the null hypothesis being that the population mean slope, $\langle \beta \rangle$, does not differ between the Intervention community and the Control community in each pair. The null hypothesis specifies $H_0:\langle \beta_{Intervention} \rangle = \langle \beta_{Control} \rangle$ but does not require that the common slope be zero; i.e., it allows for secular trend.

The community-level parameter β is to be estimated by simple linear regression. The regression slope b, fitted to one community's data, is an unbiased estimator of β and has a standard error asymptotically equal to $\sigma(KV_t)^{-1/2}$, where σ is the residual standard deviation of log delay time (y) as defined above; K is the number of cases collected in the community; and V_t is the variance of calendar time at which cases were observed. According to the study timeline described above, the observation times are expected to be uniformly distributed over an interval of L=1.5 yr, with an additional cluster at t=0 accumulated from the preceding baseline period of B=0.333 yr. The variance of this distribution is

$$V_t = \frac{L^3}{3(B+L)} - \frac{L^4}{4(B+L)^2} = 459/1936 = 0.237 \text{ yr}^2.$$

Measurement error is not the only source, and possibly not even the dominant source, of random variability in the measured slope b. The underlying "true" slope in the community will differ in a systematic way, if the experiment is successful, between the Intervention group and the Control group, but it will undoubtedly vary as well from one community to another within each group. This variability may be modeled by a random effect superimposed on the fixed effect of REACT Intervention. Assuming the true slopes are normally distributed about their REACT-group means $\langle \beta_{Control} \rangle$ and $\langle \beta_{Intervention} \rangle$ with

Version 07/01/96

variance σ_{β}^2 , the total variance of estimated slope is

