In the early design phase of REACT, the prospect of a demanding logistical effort raised the question of random subsampling of cases in the larger communities. Three schemes for sampling are detailed in Table 6. Scheme A ("All") is complete sampling. In Scheme B ("Biggest/2"), only the two largest communities (Worcester, MA, and Eugene, OR) are subsampled, at 50%. This is the closest scheme to what we expect will be required for adequate sample size, and it is the scheme that will be implemented initially. In Scheme C ("Catch 700") the target is to collect approximately 700 cases in each community. In the smallest communities, where fewer than 1000 cases are expected, 100% sampling is required. In the intermediate-sized communities (1100-2000 cases expected), 50% sampling would be employed. In the largest communities (2100-2600 cases expected), the sampling fraction would be 25%. This scheme might be adopted if event rates are higher than the current projection.

At the individual level, if all sites are pooled, subsampling skews the ethnic composition of the overall REACT sample to some degree. These effects are detailed in Table 7. It should be emphasized, however, that a valid random subsampling scheme would not alter the ethnic balance of the sample collected in any given community. Since all primary and secondary REACT analyses, in keeping with the community randomization design, are planned at the community level, these would not be biased by subsampling.

B. Detectable effect, primary analysis

Sample size is essentially fixed in advance at both levels of REACT, on the community level at 10 pairs and at the individual level by the available number of cases or some convenient sampling fraction. The effect of the REACT Intervention in reducing delay time is by contrast difficult to predict, because comparable interventions have not previously been conducted. As a consequence, power calculations for REACT are most informatively framed with sample size, power, Type I error, and variance as fixed parameters (or, in sensitivity analysis, as independent variables) and detectable effect as the dependent variable. The requisite formulas are derived in this section. The results are tabulated and discussed in

Community	410/411,	410/411,	410/411,	
	Scheme	Scheme B	Scheme C	
	A ("All")	("Biggest/2")	("Catch700")	
Alabama				
Anniston (Calhoun Co.)	1100	1100 (100%)	550 (50%)	
Tuscaloosa (Tuscaloosa Co.)	1650	1650 (100%)	825 (50%)	

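### Table 5 uses one common case count where the variance formula needs each community's own, so its detectable effects are somewhat too favourable for a given average

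*Protocol*

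**What the plan says.** - **Formula (X.B, repeated in Appendix C, section B).** The variance of the mean slope difference contains the sum of 1/K over the intervention and control community of every pair, "where J=10 is the number of community pairs".
- **Table 5 (X.C).** One K of 800, 600 or 400 is used for all 20 communities, at "80% power, 5% Type I error (two-sided"). For 600 the text gives 27-30 min at a median delay of 2.5 h and 32-35 min at 3 h. It describes this case as follows: "In the conservative case (600 per community), which should be easily attained with the broadened eligibility criteria".
- **Summary (X.C).** An effect of 30-40 min is said to be detectable with 80% power whatever sample size is attained.
- **Projected counts (Tables 4 and 6).** ICD 410/411 discharges range from 345 (Shoreline) to 2578 (Worcester). Scheme B halves only Worcester and Eugene, which leaves 345 to 1833. Appendix C, section A, says of it: "This is the closest scheme to what we expect will be required for adequate sample size". It is also the scheme to be used first.
- **Smallest communities (X.A).** For two Washington and all four Texas communities, "100% sampling will certainly be required throughout REACT".
- **Balance (XI.A.4).** Imbalance is expected, yet the plan relies on "a sampling scheme designed to obtain essentially equal numbers of cases in each community".
- **Expected yield (X.A).** After eligibility was broadened, 750 usable cases per community are expected on average, 15,000 in all.

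**The concern.** When a variance depends on the sum of 1/K, precision is set by the harmonic mean of the community sizes. With unequal sizes this is below the arithmetic mean. Entering one common K therefore understates the variance for any given average. The primary test has only 9 degrees of freedom, and the smallest communities cannot be raised because they are already fully sampled. The stated detectable effects for the primary endpoint, and the 80% attached to them, would then be too favourable. The Coordinating Center would also lack the figures it needs when deciding on the mid-course sampling changes that X.A allows.

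**Working it through.** **Inputs.** J = 10 pairs, 9 df, two-sided 5%, 80% power. Residual spread: "95% of delay times fall between 1/9 of the median value and 9 times the median value", so σ = ½·log10(9) = 0.477. Timing: "the observation times are expected to be uniformly distributed over an interval of L=1.5 yr", with a baseline of 0.333 yr placed at time 0. R_β is 1.05 or 1.15 and ρ is 0 to 0.4 (Table 8).

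**Formulas (X.B and Appendix C, section B).**
- V_t = 1.5³/(3×1.833) − 1.5⁴/(4×1.833²) = 0.6136 − 0.3766 = 0.237
- σ_β = log10(R_β)/(2×1.5) = 0.0071 or 0.0202
- SE² = 2σ_β²(1−ρ)/10 + σ²·Σ(1/K)/(V_t×100)
- Detectable slope = SE×(2.262 + 0.883) = 3.146·SE; reduction = 1 − 10^(−1.5×slope)

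**Step 1: reproduce the plan.** With K=600 throughout, Σ(1/K) = 20/600 = 0.0333.
- Best case (R_β 1.05, ρ 0.4): SE = 0.0181, slope 0.0568, reduction 17.8%, or 26.7 min (2.5 h) and 32.1 min (3 h).
- Worst case (R_β 1.15, ρ 0): SE = 0.0201, slope 0.0631, reduction 19.6%, or 29.4 and 35.2 min.

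These match Table 5, as do the rows for 800 and 400. Noncentral-t power is 79.9%. Table 5 therefore assumes equal K.

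**Step 2: use the projected proportions.** The Scheme B counts have arithmetic mean 1083 and harmonic mean 850, a ratio of 0.78. Scaled to a mean of 600, they run from about 191 to 1016 with harmonic mean 471, so Σ(1/K) = 20/471 = 0.0425.
- Best case: SE = 0.0203, reduction 19.8%, or 29.7 and 35.7 min. Power at the Table 5 effect is 70.1% (noncentrality 0.0568/0.0203 = 2.79).
- Worst case: SE = 0.0221, reduction 21.4%, or 32.1 and 38.5 min. Power is 71.8% (0.0631/0.0221 = 2.85).

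A simulated paired t-test with unequal pair variances gives 71.0-72.4%.

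**Step 3: other readings, all at the Table 5 effects for K=600.**

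| Projected cases | Mean | Harmonic mean | Power |
|---|---|---|---|
| Scheme A proportions | 600 | 440 | 67-69% |
| Scheme B proportions | 600 | 471 | 70-72% |
| Scheme C proportions | 600 | 562 | 77-78% |
| Table 4 × 750/1202, no subsampling | 750 | 550 | 76-77% |
| The same yield with Scheme B | 676 | 530 | 75-76% |
| Scheme B rescaled | 750 | 589 | 79% |
| Table 1 counts, with or without Scheme B halving | 600 | 557 or 535 | 75-78% |
| Table 1 counts, with or without Scheme B halving | 750 | 697 or 669 | 83-85% |

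The Table 1 rows add the 410 and 411 columns. One Alabama row is broken in the extracted text, so that community was given its pair partner's count.

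**Step 4: the K=400 rows.** At a Scheme B mean of 400 the harmonic mean is 314. The detectable effect is about 36-37 min (2.5 h) or 43-45 min (3 h), against 32-34 and 38-41 in Table 5.

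**Step 5: can every community reach 600?** At 750/1202 = 0.624 of the Table 4 counts, 8 of 20 fall short even with full sampling: Shoreline 215, Olympia 220, Tyler and Lake Charles 343 each, Pittsfield/Dalton 453, Brownsville and Laredo 457 each, Westfield/W. Springfield 497.

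**The case against.** Several points on the other side have weight.

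- **The plan expects 750, not 600.** This stands. At the expected yield the shortfall is smaller (75-79%). With Scheme B at that yield, the detectable effects are about 28-31 and 34-37 min, only 1-2 min above those stated. A mean near 600 is still not arbitrary: the Scheme B average of 1083 times the Table 8 attrition factors (0.85 × 0.85 × 0.75, using 90% and 60% validation on an even case mix) is 587.
- **The counts describe the earlier 410/411 population.** This stands. No community counts are given for the broadened cardiac-discharge population, so proportional scaling is an assumption.
- **Table 1 gives less unequal counts.** This also stands. With Scheme B halving, its harmonic-to-arithmetic ratio is about 0.93, and at a mean of 750 power exceeds 80%.
- **Per-community figures elsewhere in the protocol are averages**, for example 1202 in Table 4. Read as an average, 600 against an expected 750 is attainable. A reader might infer from Step 5 that the attainability statement is simply false, but it fails only if 600 is needed in each community.
- **Imbalance is acknowledged and sampling is adjustable.** This is true, and Scheme C would even the sizes out. However, it does so by sampling the larger communities down, and no power figure in the protocol reflects any imbalance.

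None of this rescues the use of one common K in a formula written with a separate K for each community.

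**Conclusion.** The point holds as a correctable error in the power section. For a given average, the Table 5 effects are too favourable whenever community sizes differ, and both sets of projections in the protocol do differ. If usable cases scale with the Table 4 and 6 counts, power at the K=600 effects is about 70-72% at a Scheme B mean of 600, 67-78% across Schemes A to C at that mean, and 75-79% at the expected yield.

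Two stronger readings are tempting but unsupported. One is that the trial's power is 70-72% without qualification. That figure needs a mean of 600 and Scheme B proportions, and the Table 1 counts at a mean of 750 put power above 80%. The other is that the trial misses its 30-40 minute target. At a Scheme B mean of 600 the detectable effects of 30-32 and 36-39 min remain within it. What does fail is the claim that the target holds at any attained sample size: at a Scheme B mean of 400 and a median of 3 h, the detectable effect is 43-45 min. Table 5 as printed already reaches 41 min in its worst row.

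**What to change.** 1. Recompute Table 5, Tables 9 and 10, and the K=600 and K=400 rows of Table 11 with projected counts for each community under the scheme in force, using the sum of 1/K already in X.B. The K=200 and K=100 rows of Table 11 describe telephone samples fixed at the same size in every community, so a common K suits them if those sizes are reached.
2. State the assumed usable yield for each community in the broadened population, reconcile Table 1 with Table 4, and show the range of results. The figures above are conditional and should not be entered as fact.
3. Say in X.C whether 600 is an average or a minimum in each community.
4. Correct the statement of essentially equal numbers in XI.A.4, and the X.C summary that the target holds whatever the attained sample size.

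The cost is a recalculation and a slightly less favourable stated figure. No extra patients and no design change are needed.
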